#### 6.6 Early Discontinuation of Treatment Allocation

The participant is free to choose to discontinue the trial treatment allocation at any time but they should always be encouraged, if they are willing, to remain in the trial and allow follow up data to be collected. However, if they do not wish any further data to be collected, this decision must be respected and the participant will be withdrawn from the trial completely. In either case, the appropriate CRF (treatment allocation Discontinuation or Withdrawal) must be completed. See Sections 5.5, 5.6 and 5.8.

Any data and samples already collected will be retained and analysed unless the participant specifically refuses to allow this. Participants should be discouraged from withdrawing consent to the use of data already collected.

Participants who discontinue treatment allocation during cycle 1 will be replaced.

#### 6.7 Loss to Follow-Up

Participants who are unavailable for assessment at the end of cycle 2 will be deemed to be have been lost to follow-up. Such participants will not be replaced unless they are lost to follow-up prior to commencement of cycle 2; this is anticipated to be likely to affect a very small number of participants.

#### 6.8 Trial Closure

The trial will be closed when all participants have been recruited and have completed the trial intervention period.

# 7. Safety Reporting

The principles of ICH GCP require that both investigators and sponsors follow specific procedures when notifying and reporting adverse events or reactions in clinical trials. These procedures are described in this section.

#### 7.1 Definitions of Adverse Events

The definitions to be applied to adverse events recorded in this trial are given in Table 7a below. As this is a trial using red cells, events of interest are those related to red cell transfusion, which are also study outcomes and will be reported separately.

**Table 7a: Definitions** 

Term	Definition
Adverse Event (AE)	Any untoward medical occurrence in a patient or clinical trial
	subject to whom a blood component has been administered.
Transfusion Related	Any untoward and unintended response to a transfused blood
Adverse Reaction or	component.
Event	
Serious Adverse Event	Respectively any adverse event, adverse transfusion reaction
(SAE) or Serious	or unexpected adverse transfusion reaction that:
Transfusion related	results in death*
Adverse Reaction	is life-threatening**
	requires hospitalisation or prolongation of existing
	hospitalisation***
	results in persistent or significant disability or incapacity
Unexpected Adverse	An adverse reaction, the nature or severity of which is not
Transfusion Reaction	consistent with the known reactions to transfusion of a blood
	component (in the case of this trial, red blood cells). Expected
	red blood cell transfusion reactions are listed in section 7.3.3.1.

\* Death due to the underlying disease or associated conditions will not be reported as an SAE.

#### 7.2 Adverse Events that do not Require Reporting

Any event that does not meet the definition of serious does not need to be recorded for this trial.

Participants in this study have a bone marrow failure disorder and some may have comorbidities. Some of these patients will be expected to develop SAEs during the course of the study, many of which will be unrelated to trial interventions. These events are not required to be reported as SAEs, however we will be capturing the listed events below in the CRF. Similarly disease progression, or death as a result of disease progression, are not considered to be SAEs and should be reported on the end of study form.

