#### 1.5 Risks and anticipated benefits

The risks associated with the trial are small. We are not testing a novel treatment nor the efficacy of an existing treatment in a new setting. The proposed transfusion thresholds are within the ranges of current practice and within the ranges described by guidelines. There may be benefits including:

- reduced risk of complications associated with use of liberal red cell transfusion policies;
- the provision of randomised evidence to address this area of clinical uncertainty;
- saving the costs of blood that is not used for transfusion and treatments of complications that are avoided.

Potential harms include the possible risk of receiving an unnecessary red cell transfusion in the liberal arm or the possible adverse effects of not receiving a red cell transfusion when it may have benefits in the restrictive arm. The fact that our thresholds are already part of existing routine care means, it is reasonable to ask participants to accept the possibility of randomisation to either transfusion policy which they may receive in any case outside of the trial setting.

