#### 5.4 Duration of randomisation

The first transfusion policy should be followed from at or before day 5 (from start of chemotherapy) of cycle 1 until the end of their first cycle of treatment. The alternate transfusion policy should be followed for the second cycle of treatment. The two cycles should be consecutive courses of intensive chemotherapy. The intention is to undertake the trial over periods of observation for predominantly inpatient stays. It is recognised that some patients may receive intensive therapy as an outpatient but the trial protocol will continue to be applied as far as possible.

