#### **Expected SAEs:**

- Admission to the intensive care unit
- Severe sepsis
- Major organ dysfunction (single or multi-organ)

\*\*The term 'life-threatening' in the definition of 'serious' refers to an event in which the patient was at risk of death at the time of the event; it does not refer to an event which hypothetically might have caused death if it were more severe.

\*\*\*Hospitalisation is defined as an inpatient admission, regardless of length of stay, even if the hospitalisation is a precautionary measure for continued observation. Hospitalisations for a pre-existing condition (including elective procedures that have not worsened) do not constitute an SAE.

- Transient ischaemic attack, Thromboembolic and ischaemic events (myocardial infarction, stroke, pulmonary embolus, DVT)
- Acute transfusion reactions to red cell blood components including indicators of transfusion associated circulatory overload (TACO) and transfusion related acute lung injury (TRALI) i.e. Congestive cardiac failure, Pulmonary oedema (definitions as described in SHOT)

If an adverse event meets the definition of an SAE and it is considered unexpected it must be recorded on an SAE form and be faxed / e-mailed to the CTU within 24 hours of the site becoming aware of it.

As this is a trial of a blood component, it is not appropriate to assess causality of any SAE and there is no requirement on the form to do so. However, any red cell transfusion reactions that occur must have their imputability assessed using the definitions in Table 7b below. There are five categories: N/A = Not assessable 0 = Excluded or unlikely, 1 = Possible, 2 = Likely (probable), and 3 = Certain. The severity of any red cell transfusion reaction will also be graded using SHOT criteria as 1 = mild, 2 = moderate or 3 = severe Two clinicians sitting on the TMG will independently review this data at the end of the study.

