#### 9.2.3 Clinical Outcomes

- Death: All-cause mortality at 3 months post study completion
- **Bleeding**: Clinically significant bleeding events are defined as equivalent to WHO Grade 3 or 4. These events will be captured using definitions applied for bleeding assessments conducted using a tool based upon that used in the TOPPS trial and further developed by an international working group the BEST collaborative.
- Proportion of participants experiencing thromboembolic and ischaemic events:
   Includes myocardial infarction, stroke, pulmonary embolus, clinically overt and line-related thrombotic events. Line related blockage may have other causes related to the type of line used. (These thromboembolic and ischaemic events may be related to higher haemoglobin concentrations, although MI may occur more commonly with lower thresholds)
- Syncopal events
- Transfusion reactions
- Length of hospital stay
- Proportion of participants with at least one blood culture verified bacterial infection

- Median EQ-5D-5L Visual Analogue Scale score for symptomatic and nonsymptomatic transfusions
- Health related quality of life at baseline, middle and end of each cycle using EQ-5D-5L/ EORTC QLQ C30 forms)

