The mean EQ-5D-5L and EORTC QLQ C30 scores for each arm will be calculated and compared at baseline and after each chemotherapy cycle. Clinically meaningful improvement will be defined as ≥0.08 on the calculated health utility EuroQOL-5D score and ≥10 points on the EORTC QLQ-C30 score (for all scores apart from fatigue and dyspnoea, for which an improvement is ≤-10). In addition to aggregate data, the percentages of participants individually achieving a clinically meaningful improvement, at any time point, compared to the baseline score (the first QoL questionnaire at randomisation), in each of the two strategies will be compared.

For other and safety analyses, data from all randomised subjects will be evaluated and descriptive statistics presented. Key clinical characteristics of enrolled participants will be compared against all recruits to AML 18 and 19 trials. The extent of exposure will be summarised (median RBC and platelet units transfused during each chemotherapy course), as well as the clinical course, such as interval between transfusions and transfusion reactions. The incidence of WHO Grade 3 or 4 bleeding and death will be summarised by treatment strategy, and length of hospital stay compared. Comparisons will be made between the two haemoglobin concentration threshold transfusion strategies. Any adverse events potentially related to the transfusion threshold such as cardiac ischaemic events, congestive heart failure, strokes (cerebrovascular accidents, CVA), thromboembolic or syncopal events, will be summarised and compared between the two arms.

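### Section 7.2 waives recording of all non-serious events, yet syncope and line-related thrombosis are clinical outcomes without a seriousness limit and have no named collection route when not serious

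*Protocol*

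**What the plan says.** **Recording rule.** Section 7.2 opens with "Any event that does not meet the definition of serious does not need to be recorded for this trial". This waives recording itself, not only expedited reporting, and no exception follows for events that are also outcomes.

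**Seriousness.** Table 7a counts an event as serious if it causes death, is life-threatening, "requires hospitalisation or prolongation of existing" hospitalisation, or leaves lasting or significant disability. Its footnote counts any inpatient admission, even a precautionary one.

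**Outcomes.** Section 9.2.3 lists "Syncopal events" as an item of its own. It also includes line-related thrombotic events in the thromboembolic and ischaemic outcome. Neither carries a seriousness limit. Section 9.4 says that adverse events potentially related to the threshold, among them "thromboembolic or syncopal events, will be summarised and compared between the two arms".

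**Setting and blinding.** Section 5.4: "The intention is to undertake the trial over periods of observation for predominantly inpatient stays". Section 5.6 says that physicians know the allocation.

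**The concern.** Section 9.4 commits the trial to a comparison, while section 7.2 tells sites that part of the data for it is optional. A site that follows 7.2 literally meets the protocol and still hands over incomplete counts of syncope and line-related thrombosis. No analysis plan can recover events that were never written on a form.

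The comparison matters because section 1.5 names, as a potential harm, the "possible adverse effects of not receiving a red cell transfusion when it may have benefits in the restrictive arm". Syncope is a plausible sign of that harm. Section 9.3 says the study is meant to help plan a definitive trial, so an under-recorded event rate could be carried into that planning.

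**Working it through.** The protocol gives no figure to reproduce. The check traces each outcome from sections 9.2.3 and 9.4 to a place where a site is told to record it.

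| Place | Non-serious syncope | Non-serious line-related thrombosis | Mild red cell transfusion reaction |
|---|---|---|---|
| 9.2.3, outcome without a seriousness limit | Yes | Yes | Yes |
| 9.4, compared between arms | Yes | Yes, as thromboembolic | Summarised |
| 7.2, captured list (expected SAEs) | Not named | Not named; DVT and PE are | Acute reactions named |
| 7.3.1, AE form | Only if serious and listed | Only if serious and listed | Separate duty to assess imputability |
| Table 1, own row | None | None | None |
| Dedicated form | None | None | Transfusion reaction form (7.3.4) |
| General source in 9.2 | Medical records | Medical records | Transfusion registers, medical records |

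**First two columns.** Nothing in the protocol directs a site to record the non-serious case. Bleeding shows the contrast: it has a daily row in Table 1, and section 6.3 requires it to be recorded prospectively.

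**Effect of setting.** A participant who faints on the ward is already in hospital, so the hospitalisation criterion is met only if the stay is prolonged. The same faint at home followed by a precautionary admission is serious under the footnote to Table 7a. Required capture therefore depends on where the participant was.

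**What can be said about size.** Let s be the share of episodes that are serious, and v the share of non-serious episodes that sites record although they need not. Then

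captured share c = s + (1 − s) × v.

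The protocol gives neither s nor v. If s is assumed to lie between 0.10 and 0.50:

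- v = 0 gives c = 0.10 to 0.50.
- v = 1 gives c = 1.00 whatever s is.

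The captured share could thus lie anywhere from 10% to 100% under that assumption. This range shows that the loss is undetermined; it is not an estimate.

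**What it does to the comparison.** If c is the same under both strategies, the observed difference in rates is c times the true difference, and the expected ratio is unchanged: events are lost and precision falls, with no direction of bias between strategies. If staff who know the allocation record more readily under one strategy, v differs between strategies and the comparison is biased. The sign depends on which strategy gets the fuller recording, and the protocol offers nothing to settle that.

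**The case against.** The strongest reply is that 7.2 is a safety-reporting section and does not govern outcomes. It waives recording without forbidding it. Section 9.2 draws primary and secondary outcomes from several sources including medical records, and the synopsis places clinical outcomes among the secondary ones. Section 6.2.2 says nearly all source data are in the medical records. Table 1 is a summary, and length of stay and culture-verified infection also lack rows. The bracketed list after thromboembolic events in 7.2 can be read as examples, so a serious line-related thrombosis would be covered. Safety data are descriptive, and the 70% adherence criterion in 9.4 does not depend on syncope.

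Much of this stands. It limits the point to incomplete or inconsistent capture and keeps it away from the primary outcomes. A missing row in Table 1 proves little alone. For syncope and line-related thrombosis, however, it coincides with an explicit waiver and with no form or instruction to extract the event. That a faint may appear in the notes does not mean anyone is asked to find it.

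Four stronger readings are tempting, and the protocol does not support them:

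- **Most such events will be missing.** No rates are given and recording is not prohibited, so this cannot be shown.
- **Mild transfusion reactions will be lost.** A later paragraph of 7.2 requires any red cell reaction to be assessed for imputability and "graded using SHOT criteria as 1 = mild, 2 = moderate or 3 = severe", with review by two clinicians at the end. Section 7.1 says transfusion-related events are reported separately, and 7.3.4 names a form. What remains is that the opening sentence of 7.2 does not fit its own later paragraph.
- **The restrictive strategy will look safer.** This needs more syncope under that strategy, or fuller recording under the other. No figure in the protocol establishes either.
- **Table 7a excludes harm from not being transfused.** It does define an adverse event as one in a patient or "subject to whom a blood component has been administered". No causal link is required, though, and section 1.1 reports an average of 11-12 red cell units in the first course, so few participants would stay outside the definition for long.

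**Conclusion.** The point holds for non-serious syncope and non-serious line-related thrombosis. Section 7.2 makes their recording optional, sections 9.2.3 and 9.4 treat them as outcomes and compare syncopal and thromboembolic events between arms, and no list entry, form or schedule row fills the gap. Syncope is the clearer case, because line-related thrombosis can be read into the thromboembolic item when serious. The supported consequence is that these events may be captured incompletely and inconsistently by setting, site or arm. Neither the size nor the direction of any effect on the comparison can be derived from the protocol.

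The conclusion assumes that sites follow the protocol as written and that the CRFs, which are not part of the document, add no separate field for these events. If they do, only the wording of 7.2 needs correcting. The matter is a secondary one in a feasibility trial, but worth correcting because the stated comparison lacks a stated way of collecting its data.

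**What to change.** Add an exception after the opening sentence of 7.2, for example: *This does not apply to the clinical outcomes in section 9.2.3, in particular syncope and thrombotic events including line-related ones, which are recorded for every participant in each cycle whatever their seriousness. Red cell transfusion reactions of any grade are recorded as set out later in this section.*

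Add one row for these outcome events to Table 1 under Cycle 1 and Cycle 2, and a matching item on the per-cycle CRF, so that a site records yes or no and the absence of an entry can be told apart from the absence of an event.

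The cost is a short wording change, one schedule row, one CRF item and slightly more recording at sites. No procedure, treatment rule or planned analysis changes.

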#### **Expected SAEs:**

- Admission to the intensive care unit
- Severe sepsis
- Major organ dysfunction (single or multi-organ)

\*\*The term 'life-threatening' in the definition of 'serious' refers to an event in which the patient was at risk of death at the time of the event; it does not refer to an event which hypothetically might have caused death if it were more severe.

\*\*\*Hospitalisation is defined as an inpatient admission, regardless of length of stay, even if the hospitalisation is a precautionary measure for continued observation. Hospitalisations for a pre-existing condition (including elective procedures that have not worsened) do not constitute an SAE.

- Transient ischaemic attack, Thromboembolic and ischaemic events (myocardial infarction, stroke, pulmonary embolus, DVT)
- Acute transfusion reactions to red cell blood components including indicators of transfusion associated circulatory overload (TACO) and transfusion related acute lung injury (TRALI) i.e. Congestive cardiac failure, Pulmonary oedema (definitions as described in SHOT)

If an adverse event meets the definition of an SAE and it is considered unexpected it must be recorded on an SAE form and be faxed / e-mailed to the CTU within 24 hours of the site becoming aware of it.

As this is a trial of a blood component, it is not appropriate to assess causality of any SAE and there is no requirement on the form to do so. However, any red cell transfusion reactions that occur must have their imputability assessed using the definitions in Table 7b below. There are five categories: N/A = Not assessable 0 = Excluded or unlikely, 1 = Possible, 2 = Likely (probable), and 3 = Certain. The severity of any red cell transfusion reaction will also be graded using SHOT criteria as 1 = mild, 2 = moderate or 3 = severe Two clinicians sitting on the TMG will independently review this data at the end of the study.

#### 7.3 Investigator Responsibilities

The Chief Investigator (CI) has overall responsibility for the conduct of the study. As this is a multi-site study, the Principal Investigator (PI) has responsibility for the research at their local site and is responsible for informing the CTU of all reportable serious adverse events that occur at their site following the guidelines below.

#### 7.3.1 Investigator Assessment of AEs

When an AE or AR occurs, the investigator responsible for the care of the patient must first assess whether or not the event is serious using the definitions in Table 7a: definitions. If the event is serious and is on the list of expected events in section 7.1, then the details must be recorded on the AE form. If the event does not fit any of the exempted categories, it must be recorded on an SAE form and faxed to the CTU within 24 hours of becoming aware of it.

#### 7.3.2 Investigator Assessment of Transfusion Reactions

As this is a trial of a blood component, it is not appropriate to assess causality of any SAEs and there is no requirement on the form to do so. However, any transfusion reactions that occur must have their imputability assessed using the definitions in Table 7b. There are 5 categories: unrelated, unlikely, possible, probable and definitely related.

Table 7b: Definitions of Imputability

Relationship	Description	
Unrelated	There is no evidence of any causal relationship	
Unlikely	There is little evidence to suggest there is a causal relationship (e.g. the event	
	did not occur within a reasonable time after administration of the trial transfusion).	
	There is another reasonable explanation for the event (e.g. the patient's clinical	
	condition, other concomitant treatment).	
Possible	There is some evidence to suggest a causal relationship (e.g. because the event	
	occurs within a reasonable time after administration of the trial transfusion).	
	However, the influence of other factors may have contributed to the event (e.g.	
	the patient's clinical condition, other concomitant treatments).	
Probable	The evidence is clearly in favor of attributing the adverse reaction to the blood or	
	blood component.	

Definitely	There is conclusive evidence beyond reasonable doubt attributing the adverse
	reaction to the blood or blood component.

#### 7.3.3 Expectedness of Transfusion Reactions

If the event is a Serious Transfusion-Related Adverse Reaction, the Investigator must assess the expectedness of the event. Please refer to section 7.3.3.1 for a list of expected red cell transfusion reactions. It is highly unlikely that an unexpected Serious Adverse Transfusion Reaction will occur, but the possibility must not be excluded. If a Serious Transfusion Related Adverse Reaction is assessed as being unexpected, the PI must notify the CTU.

#### 7.3.3.1 Expected red blood cell transfusion reactions

Acute transfusion reactions (ATR) are defined (according to SHOT) as those occurring at any time up to 24 hours following a transfusion of blood or components

- Anaphylactic reactions
- Moderate allergic reactions
- Hypotensive reactions
- Mixed febrile/allergic reactions

and may be due to:

- incorrect component being transfused
- haemolytic reactions
- febrile non haemolytic reaction
- transfusion-related acute lung injury (TRALI)
- transfusion-associated circulatory overload (TACO)
- transfusion-associated dyspnoea (TAD)
- bacterial contamination of the component

